### 10.3.1 Major Protocol Deviations

Subjects with major protocol deviations will be identified (at a population level) to determine whether they will be excluded from any of the analysis populations. The following have been identified as the major protocol deviations.

The categories for the major deviations will include, but are not limited to the deviations presented in Table 10.

**Table 10: Definition of Major Protocol Deviations**

Category	Description
Violation	Violation of inclusion/exclusion criteria
Mis-randomization	Being administered the wrong product according to the randomization schedule
Mis-use of product	

Use of any nicotine or tobacco-containing product other than the assigned product during the exposure period, or use of any nicotine tobacco-containing product during wash-out days (e.g., see Section 11.4 “Measurements of Product Compliance”).

Use of assigned product inconsistent with the labeled use (e.g., number of sprays of the NNS is not 2)

Concomitant medication	Use of any drugs which are known to affect CYP2A6 activity

Among the above criteria, violations of inclusion criteria 5 to 7, or of the exclusion criteria 1, 3 to 16, and 18 will be assessed for their impact on the PK population and

evaluated during the pre-analysis data review meeting (Section 6.3.2 “Methods of Assigning Subjects to Treatment Sequences”).

### 10.3.2 Minor Protocol Deviations

The categories for the minor deviations will include, but are not limited to the deviations presented in Table 11.

**Table 11: Definition of Protocol Deviation Categories**

Category	Description
Time deviation (Plasma nicotine PK sample)	Assessments not taken at the correct time or within the allowed time window or date/time is missing (see Table 12)
Time deviation (other assessment)	Assessments not taken at the correct time or within the allowed time window or date/time is missing (see Table 12)
Assessment missing (Plasma nicotine PK sample)	Assessment is missing
Assessment missing (other assessment)	Assessment is missing

#### 10.3.2.1 Assessment Windows

Smoking of the randomized product must take place within the 06:00 and 09:00 AM window at Day 1 and Day 3. The windows reported in Table 12 will be applied to the timing of data collection.

**Table 12: Definition of Assessment Windows**

Assessment	Nominal Time point(s) (relative to $T_0$ )	Window
Plasma nicotine PK sample 	First sample	Within 15 min prior to $T_0$
	2, 4, 6, 8 and 10 min	+ 1 min
	15, 30 and 45 min	+ 2 min
	60 min	+ 3 min
	2, 4, 6, 9, 12 and 24 h	+ 5 min
	First assessment	Prior to product use
Assessment of cough	24 h after $T_0$	- 5 min
QSU-brief	First time	Within 15 min prior to $T_0$
	15 min, 30 min, 45 min, 1 h and 2 h	+10 min
	4, 6, 9 and 12 h	
COHb blood sampling	First sample	Within 15 min prior to $T_0$
	15 min	+ 2 min
	60 min	+ 3 min
	4 and 12 h	+ 5 min

CO breath test	First measurement	Within 15 min prior to $T_0$
	Second measurement	12:00-01:30 PM
	Third measurement	04:00-05:30 PM
	Fourth measurement	08:00-09:30 PM
CYP2A6	COT and HCOT measurements	Prior to Smoking

 Note that cotinine will be measured together with nicotine at all the corresponding time points. However, only the data from the three following time points: prior  $T_0$ ,  $T_0 + 12$  h,  $T_0 + 24$  h will be used for analysis

## 11 PLANNED STATISTICAL METHODS

### 11.1 General Considerations

Data analysis will be performed using SAS® Version 9.2 or higher.

Data listings will be provided for all data collected as required by this protocol, ordered by sequence, product, subject and time point (if applicable), unless otherwise stated. Summary statistics and statistical analysis will only be presented for data where detailed in this SAP. All unscheduled assessments will be included in the listings.

Safety data will be summarized for the safety population, PK data will be summarized and analyzed for the appropriate PK population, biomarker data will be summarized and analyzed for the PK populations unless otherwise stated.

#### 11.1.1 Stratified Presentation

Data summaries will be produced by sequence, sex (male and female), mCC nicotine level at Admission (ISO nicotine level  $\leq 1$  mg and  $> 1$  mg) as reported on the pack, and time point (if applicable), unless otherwise stated.

Stratified presentations will be conducted on the PK populations for the following endpoints:

- Demographics.
- PK parameters, during single use day.
- Nicotine and Cotinine concentrations in blood.
- COHb and CO values, during single use day.
- MCEQ and QSU-brief questionnaires, during single use day.

Cotinine levels will also be summarized by race (White, Black or African American, American Indian or Alaska Native, Asian, Native Hawaiian or Other Pacific Islander, Other).

#### 11.1.2 Subgroup Analyses

Exploratory subgroup analyses will be conducted for the primary endpoints in the following planned subgroups: sex (male or female), mCC nicotine level at Admission (ISO nicotine level  $\leq 1$  mg and  $> 1$  mg) provided there are greater than 4 subjects in each category.

### 11.1.3 Descriptive Statistics

For continuous data, summary statistics will include the number of subjects, the number and percent of subjects with missing data, the arithmetic mean, arithmetic standard deviation (SD), median, first and third quartiles, minimum, maximum, and number; for log-normal data (e.g., the PK parameters: AUC and  $C_{max}$ ) the geometric mean and geometric CV will be presented instead of the arithmetic mean and SD. For categorical data, frequency counts and percentages will be presented.

Data listings will include all subject-level data collected as defined in the protocol.

Summary statistics and statistical analyses will be performed for subjects included in the relevant analysis population. For the calculation of summary statistics and statistical analysis, unrounded data will be used.

Summaries on PK population will be produced by analysis group, and overall if applicable.

Summaries on Safety population will be produced overall and by sequence, including the available data from subjects who tested the product but were not enrolled or were discontinued from enrolment before randomization. Data collected at discharge visit will be reported at Day 4/Discharge.

The following product labels and sequence descriptions will be used throughout the TFLs (Table 13) :

**Table 13: Product and Sequence Labels**

Product	Format used in TFLs	Order in TFLs
Tobacco Heating System 2.2	THS 2.2 Menthol	1
Menthol		
Menthol conventional cigarettes	mCC	2
Nicotine nasal spray	NNS	3
Sequence		
THS 2.2 Menthol then mCC	THS 2.2 Menthol - mCC	1
mCC then THS 2.2 Menthol	mCC – THS 2.2 Menthol	2
THS 2.2 Menthol then NNS	THS 2.2 Menthol - NNS	3
NNS then THS 2.2 Menthol	NNS – THS 2.2 Menthol	4

The following stratification labels (Table 14) for the TFLs will be used:

**Table 14: Stratification Labels**

Stratification Factor	Definition
Sex	male female
ISO nicotine level	$\leq 1$ mg $> 1.0$ mg

### 11.1.4 Definitions for Statistical Data Analysis

The following definitions (Table 15) for statistical analyses/presentations will be used:

**Table 15: Timepoint Definitions**

Term	Definition
Baseline	Baseline will be the last available time point prior to the product test (THS 2.2 Menthol or NNS) at Admission (Day -1)
$T_0$	The time of the product use on Day 1 and Day 3. Start of product use for THS 2.2 Menthol is defined as the time of the first puff. The start time for mCC corresponds to the lighting of the mCC, and the start time of the NNS product is the time of the spray in the first nostril.

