6.3.1 Admission (Day -1)

Subject will be instructed not to smoke in the morning prior to Admission. Smoking *ad libitum* will be allowed throughout the day of admission except during the procedures until 11:00 PM. All subjects will be allowed to continue smoking *ad libitum* their own mCC. All subjects (except women with a positive pregnancy test at Screening or Admission) will undergo a THS 2.2 Menthol test first and subsequently a NNS test at Day -1 prior to enrolment.

Following agreement that the THS 2.2 Menthol is acceptable, subjects will be randomized to one of 4 product exposure sequences using an Interactive Web Response System.

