6.3.2 Investigational Period (Day 0 to Day 3)

During the first washout, each subject will maintain nicotine abstinence from Day -1 at 11:00 PM to the time of single use of his/her allocated product at Day 1. At Day 1, after the single use of the product, subjects will maintain nicotine abstinence for the rest of the day. During the second washout on Day 2, subjects will maintain nicotine abstinence until the time of single use of his allocated product at Day 3. Subjects will not be allowed to smoke or use any other nicotine/tobacco-containing products other than the products they are allocated to.

Time point 0 will be defined as start of the single product use on the single use days or as start of the first product use on each study day. The start of product use for THS 2.2 Menthol is defined as the time of the first puff. The start time for mCC corresponds to the lighting of the mCC, and the start time of the product is the time of the spray in the first nostril. The 30 seconds it takes to pre-heat the tobacco stick holder will not be taken into account. **The subject must not take a puff of the tobacco stick during the pre-heating time.**

The start of the first product use can be different for each subject both days of product use. However, it must be in the window of 6:00 AM to 9:00 AM.

Confidentiality Statement: Data and information contained in this document are considered to constitute trade secrets and confidential commercial information, and the legal protections provided to such trade secrets and confidential information are hereby claimed under the applicable provisions of United States law. No part of this document may be publicly disclosed without the written consent of Philip Morris International.

Single use of products (Day 1 and Day 3)

On Day 1 and Day 3, subjects will use the product they are randomized to only once in the morning between 6:00 AM to 9:00 AM, and will abstain from the product or other nicotine/tobacco-containing items for the rest of the day, i.e., subjects in the THS 2.2 Menthol arm will use one Menthol Tobacco Stick, subjects in the mCC arm will smoke one mCC, and subjects in the NNS arm will spray once into each nostril (leading to an estimated total administered amount of 1 mg nicotine), as shown:

	Sequence 1	Sequence 2	Sequence 3	Sequence 4
Day 1	THS 2.2 Menthol	mCC	THS 2.2 Menthol	NNS
Day 3	mCC	THS 2.2 Menthol	NNS	THS 2.2 Menthol

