7.4.8 Vital Signs

Systolic and diastolic blood pressure, pulse rate, and respiratory rate will be measured at the Screening Visit, at Admission, and at every day in confinement. All parameters will be recorded in supine position after the subject has rested for at least 5 minutes.

For every measurement, it has to be documented if the subject has smoked within 15 minutes prior to the measurement.

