9.2 Admission

The following assessments will be performed at Admission (Day -1) (Table 5):

Table 5. Time Schedule – Day -1 Admission

Time	Blood sample	Procedures	Additional information
Start of procedure			
		AE/SAE recording, concomitant medication	All day
		Advice on the risks of smoking and debriefing	
		Readiness to accept interruptions of smoking for up to 4 days	
	√	trans -3'-hydroxycotinine and cotinine (CYP2A6 activity) in plasma	The subject should not have smoked in the morning until this assessment Must be done prior to smoking
		Spirometry	Has to be done prior smoking
6:30 AM		Beginning of smoking period	
		Urine pregnancy test for all female subjects	
	√	Clinical laboratory parameters (hematology, urine analysis, clinical chemistry)	In at least 10 hours of fasting
		Urine cotinine screening test	
		Urine drug screen	
Prior to 10:00 AM		Breakfast	
Prior to 11:30 AM		Vital signs	At least 5 min in supine position prior to measurement
Prior to 11:30 AM		Physical examination, weight and calculated BMI	
Prior to 11:30 AM		Identification of current mCC brand	
Prior to 11:30 AM		Smoking history	
Prior to 11:30 AM		Alcohol breath test	
Prior to 11:30 AM		CO breath test	
Prior to 2:30 PM		Lunch	

Confidentiality Statement: Data and information contained in this document are considered to constitute trade secrets and confidential commercial information, and the legal protections provided to such trade secrets and confidential information are hereby claimed under the applicable provisions of United States law. No part of this document may be publicly disclosed without the written consent of Philip Morris International.

afternoon	Snacks	
4:30 PM-6:00 PM	Product test for THS 2.2 Menthol and NNS	The THS 2.2 Menthol test should be done first and then the NNS test
4:30 PM-6:00 PM	Inclusion/exclusion criteria	
4:30 PM-6:00 PM	Enrolment	
In the evening prior to 9:00 PM	Dinner	
11:00 PM	End of smoking period	

Abbreviations: AE = Adverse event; BMI = Body mass index; CC = conventional cigarette(s); CO = Carbon monoxide; CYP2A6 = Cytochrome P450 2A6; NNS = Nicotine nasal spray; SAE = Serious adverse event; THS = Tobacco Heating System

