12.1.2 Definitions for Statistical Data Analysis

Unless otherwise stated, for the purposes of statistical analyses, baseline is defined as the last available time point prior to T_0 on Day 1, from 6:00 AM to 9:00 AM.

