#### 11.6.4.5.3 Vital Signs

Systolic and diastolic blood pressure, pulse rate and respiratory rate measured during the study will be listed by sequence and study day.

Descriptive statistics will be presented for supine systolic and supine diastolic blood pressure, pulse rate and respiratory rate at baseline, and on every subsequent day of the confinement period by sequence and overall for each study day. Vital signs data will be summarized together with changes from baseline.

The data will be presented in the below outputs:

TFL number	Title
<hr/>	
TABLES	
15.2.6.13	Summary of Supine Vital Signs – Safety Population
<hr/>	
LISTINGS	
15.3.6.7	Listing of Vital Signs Data and Changes from Baseline

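### SAP Table 15 moves baseline to Admission day without listing the change, so vital-sign changes on Days 1 and 3 mix any response to single use with any shift from abstinence

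*SAP*

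**What the plan says.** Protocol 12.1.2 gives a default, subject to exceptions stated elsewhere: "baseline is defined as the last available time point prior to T_0 on Day 1, from 6:00 AM to 9:00 AM". SAP 11.1.4 (Table 15) replaces it: "Baseline will be the last available time point prior to the product test (THS 2.2 Menthol or NNS) at Admission (Day -1". SAP Section 9, which sets out changes from the protocol's analysis, covers by-product safety summaries, shift tables, interaction terms and cotinine, but not baseline.

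For vital signs, SAP 11.6.4.5.3 plans descriptive statistics at baseline and on each later confinement day, by sequence and overall, and adds: "Vital signs data will be summarized together with changes from baseline". These go into Table 15.2.6.13 and Listing 15.3.6.7.

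On smoking, Protocol 6.3.1 says that ad libitum smoking "will be allowed throughout the day of admission except during the procedures until 11:00 PM". The Day -1 schedule in Protocol 9.2 puts "Beginning of smoking period" at 6:30 AM and vital signs at any time before 11:30 AM. For every vital-sign measurement, Protocol 7.4.8 says that "it has to be documented if the subject has smoked within 15 minutes prior to the measurement"; smoking in that interval is recorded but not forbidden. Protocol 6.3.2 then has "each subject will maintain nicotine abstinence from Day -1 at 11:00 PM to the time of single use" on Day 1.

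**The concern.** A change from baseline on a single-use day is naturally read as what happened after the product was used. That reading works if the baseline was taken in the state the subject was in just before use. Here the subject enters each single use after a nicotine wash-out, while the reference value comes from a day on which smoking was allowed. Two things differ between the two readings: the product use and the period of abstinence. The reported change cannot separate them.

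At stake is what the vital-sign table can show. SAP Section 9 has dropped by-product safety summaries, so the display by sequence and study day is the main quantitative view of vital signs after each use. A real response could be hidden, or an apparent one created, depending on which way the abstinence shift goes. Readings taken in abstinence at the same clock time already exist, but no change from them is planned.

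**Working it through.** The plan states no figure to reproduce. The check compares the two definitions with the assessment schedule.

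**1. Which variables are affected.** Laboratory tests and spirometry have no scheduled reading between Day -1 and T0 on Day 1, so both definitions give Day -1. ECG has none between Screening and Day 1, so both give Screening, as SAP 11.6.4.5.5 states. Vital signs are taken daily. Protocol Table 8 schedules none before T0 on Day 1, so the protocol's baseline falls back to the Day 0 reading; the SAP's is Day -1.

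**2. Clock times.** Inputs: ad libitum smoking ends at 11:00 PM on Day -1 (Protocol 6.3.2); T0 is 6:00-9:00 AM on Days 1 and 3; vital signs are at 10:00-11:30 AM on Days 0, 1, 2 and 3 (Protocol Tables 6, 7 and 8).

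| Reading | Hours from end of ad libitum smoking | Hours from latest product use |
|---|---|---|
| Day -1 (SAP baseline) | at least 11.5 h before | not applicable |
| Day 0 | 11 to 12.5 h after | not applicable |
| Day 1 | 35 to 36.5 h after | 1 to 5.5 h after Day 1 T0 |
| Day 2 | 59 to 60.5 h after | 25 to 29.5 h after Day 1 T0 |
| Day 3 | 83 to 84.5 h after | 1 to 5.5 h after Day 3 T0 |

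For example, from 11:00 PM on Day -1 to 10:00 AM on Day 1 is 1 + 24 + 10 = 35 h. From T0 at 9:00 AM to a reading at 10:00 AM is 1 h; from 6:00 AM to 11:30 AM is 5.5 h.

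**3. What each change contains.** Let P be the mean response to single use at the time of the reading. Let W be the mean shift due to abstinence between Day -1 and that reading (it may differ between Day 1 and Day 3). Let f be the share of W already present at the preceding wash-out reading.

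- Change from the SAP baseline = P + W
- Change from the preceding wash-out day = P + (1 - f)W

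**4. Illustration.** The documents give no value for P, W or f, so all three are assumptions. With P = +3:

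| Assumed W | From Day -1 | From wash-out day, f = 1 | From wash-out day, f = 0.5 |
|---|---|---|---|
| +5 | +8 | +3 | +5.5 |
| 0 | +3 | +3 | +3 |
| -2 | +1 | +3 | +2 |
| -5 | -2 | +3 | +0.5 |
| -10 | -7 | +3 | -2 |

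For W = -5: from Day -1, 3 - 5 = -2; from the wash-out day with f = 0.5, 3 + 0.5 × (-5) = +0.5.

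**5. How good the wash-out references are.** With the half-life of about 2 h in Protocol 4.2, Day 0 is 11/2 = 5.5 to 12.5/2 = 6.25 half-lives after smoking ends, leaving about 2.2% to 1.3% of nicotine. SAP 11.4 still expects exhaled CO above 10 ppm on Day 0, so f may be below 1 there. Day 2 is 12.5 to 14.75 half-lives after the single use on Day 1 and is the stronger reference.

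**The case against.** The strongest defence is that the SAP baseline suits the stated aim. That aim is to monitor safety during the study, not to estimate a product effect on vital signs. Every subject tests THS 2.2 Menthol and then NNS on Day -1, and the safety population and adverse-event summaries both count from that test. The Day -1 value is thus the last one before any study product; Day 0 comes after both. The protocol's definition is only a default. This stands, and is why the Day -1 baseline should not be discarded.

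It can also be said that the table already shows Day 0 and Day 2. With complete data, subtracting rows gives the mean change from the wash-out day. That is correct for the mean, but the spread of the paired change is not recoverable: its variance is s₀² + s₁² - 2r·s₀·s₁, and the table does not give the within-subject correlation r. Nor would it give the extremes of that change.

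Finally, readings 1-5.5 h after T0 are 0.5-2.75 half-lives after use, so no choice of baseline recovers an early peak. This stands as a limit of the schedule.

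Some stronger readings are not supported:

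- A reader might infer that Day -1 readings were taken soon after a cigarette. Subjects are told not to smoke on the morning before Admission, and the reading has no fixed relation to smoking. Its smoking state is uncontrolled, not shown to be recent smoking.
- A reader might infer that abstinence lowers pulse and blood pressure, so that a rise is masked. Neither document says so.
- A reader might infer that cough loses its baseline, being first assessed on Day 0. SAP 11.6.4.5.6 plans no change from baseline for cough, so no SAP output is altered.

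**Conclusion.** The point holds within a limited scope. The SAP departs from Protocol 12.1.2 without listing it, and for vital signs the departure changes the reference from an abstinent reading to one with uncontrolled smoking state. On Day 1 the reported change combines any product response with any shift over 35-36.5 h of abstinence. On Day 3 it does so over 83-84.5 h since ad libitum smoking, with one product use between. This follows from the schedule and needs no assumption about direction. The size of the distortion cannot be derived from the documents; the +8 to -7 range for a true +3 rests wholly on assumed shifts of +5 to -10.

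The wash-out reference should not be taken as a complete cure: on Day 1 it removes the shift only if the shift is already complete 11-12.5 h into abstinence. Nor is a planned product comparison biased, because none is planned for vital signs. A randomized contrast between sequences on Day 1 would largely cancel the shift, since abstinence histories are common up to then, but that contrast is not planned either. All 62 randomized subjects contribute to the affected summaries, which are descriptive and secondary. The primary PK analysis is untouched. This is worth correcting but does not threaten the study's conclusions.

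**What to change.** - Keep the Day -1 value in SAP Table 15 as the baseline before study-product exposure.
- In SAP 11.6.4.5.3, Table 15.2.6.13 and Listing 15.3.6.7, add the paired within-subject change from the preceding wash-out day: Day 0 to Day 1 and Day 2 to Day 3, both in the 10:00-11:30 AM window.
- Add a footnote that Day 0 is only 11-12.5 h into abstinence, so the Day 1 change may still carry some abstinence effect.
- In SAP Section 9, record that baseline differs from Protocol 12.1.2 and why.

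The cost is SAP wording and extra columns in one table and one listing. No new measurement is needed.

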### 11.1.5 Handling of Dropouts or Missing Data (including outside the limits of quantification)

Due to the nature of the measurements and the short periods of exposure and use the amount of missing data is expected to be limited. The specific imputations that will be allowed in order to analyze the data are as follows:

Questionnaire data:

- Total scores and domain or subscale scores may use a certain degree of imputation (by averaging across individual item scores) as detailed in Section 7.3 “Questionnaires”.

Laboratory parameters:

- For the calculation of summary statistics, values below the LLOQ (BLQ) will be imputed using LLOQ/2 and included in descriptive statistics. Values above ULOQ (AUQ) will be imputed as the ULOQ and included in descriptive statistics.
- Where there is No Result (NR), these are considered as missing, and will not be imputed.
- The number of values below BLQ or AUQ will be presented in each summary table.
- If 50% or more data are BLQ or AUQ, only the number (%) of BLQ or AUQ values will be reported in the summaries, together with minimum (if not BLQ are present) and maximum (if not AUQ are present) of the observed values.

PK timepoints:

- For time points recorded in the format hh:mm, instead of hh:mm:ss, the missing information on seconds will be imputed by 30 sec.

PK concentration data:

- LLOQ values before  $T_0$  are considered as zero.
- LLOQ values after the last quantifiable value are not included in the analysis (e.g., for the calculation of AUC).

- Any other LLOQ value (after  $T_0$  and before the last quantifiable value) would need to be queried and, if confirmed, it will be imputed by LLOQ/2.

